### **Inclusion/Exclusion Criteria**

**Inclusion Criteria:** A woman will be eligible for enrollment in this study only if all of the following inclusion criteria apply and have been met at the time of the Week 24/Baseline visit:

1. Completed 24 weeks of study drug treatment and study participation in either MVT-601-3101 or MVT-601-3102;
2. Has voluntarily signed and dated the informed consent form prior to initiation of any study-specific procedures for MVT-601-3103;

Note: Procedures conducted as part of the parent study that also serve as baseline procedures for this study will be done under the informed consent for the parent study.

3. Is not expected to undergo gynecological surgery or other surgical procedures for treatment of endometriosis (including ablation, shaving, or excision) during the study, including during the Follow-Up Period, and the patient does not desire such treatment during this time frame;
4. Has a negative urine pregnancy test at the Week 24/Baseline visit;
5. Has agreed to continue to use only study-specified analgesic medications during the study and is not known to be intolerant to these;
6. Agrees to continue to use acceptable non-hormonal contraceptive methods as described in Section 4.6 consistently during the Open-Label Treatment Period and for at least 30 days after the last dose of study drug. However, the patient is not required to use the specified non-hormonal contraceptive methods if she:
  - a. Has a sexual partner(s) who was vasectomized at least 6 months prior to the Week 24/Baseline visit;
  - b. Had a bilateral tubal occlusion (including ligation and blockage methods such as Essure™), at least 6 months prior to the Week 24/Baseline visit (patients with Essure must have prior confirmation of tubal occlusion by hysterosalpingogram) and there must be no evidence of post-Essure syndrome;
  - c. Has a non-hormonal intrauterine device (eg, Paragard®) placed in the uterus;
  - d. Is not sexually active with men; periodic sexual relationship(s) with men requires the use of non-hormonal contraception as noted above;
  - e. Practices total abstinence from sexual intercourse, as her preferred lifestyle; periodic abstinence is not acceptable.

Exclusion Criteria: None of the following criteria may be true for a patient to be eligible for enrollment into this study.

1. Has had a surgical procedure for treatment of endometriosis at any time during the parent study (MVT-601-3101 or MVT-601-3102);
2. Has any chronic pain or frequently recurring pain condition, other than endometriosis, that is treated with opioids or requires analgesics for  $\geq 7$  days per month;
3. Has a weight that exceeds the weight limit of the DXA scanner or has a condition that precludes an adequate DXA measurement at the lumbar spine and proximal femur (eg, bilateral hip replacement, spinal hardware in the lumbar spine);
4. Has a Z-score  $< -2.0$  or has a  $\geq 7\%$  decrease in bone mineral density from the parent study Baseline at lumbar spine, total hip, or femoral neck based on the parent study Week 24 DXA assessment of bone mineral density;
5. Anticipated to use any prohibited medications as detailed in Section 5.10.1;
6. Has any contraindication to treatment with low-dose estradiol and norethindrone acetate, including:
  - a. Known, suspected, or history of breast cancer;
  - b. Known or suspected estrogen-dependent neoplasia;
  - c. Active deep vein thrombosis or pulmonary embolism, or history of these conditions prior to the Week 24/Baseline visit;
  - d. History of or active arterial thromboembolic disease, including stroke and myocardial infarction;
  - e. Known anaphylactic reaction or angioedema or hypersensitivity to estradiol or norethindrone acetate;
  - f. Known protein C, protein S, or antithrombin deficiency, or other known thrombophilia


disorders, including Factor V Leiden;
 
g. Migraine with aura;
 
h. History of porphyria;
 
7. Has current active liver disease from any cause;
 
8. Has a systemic autoimmune disease (eg, systemic lupus erythematosus, Sjogren's syndrome, rheumatoid arthritis, polymyositis, systemic sclerosis, psoriasis, psoriatic arthritis, vasculitic syndromes, etc); psoriasis not requiring or anticipated to require systemic therapy is permitted;
 
9. Had any of the following clinical laboratory abnormalities at the parent study Week 20 visit or, if available, any subsequent visit in one of the parent studies (MVT-601-3101 or MVT-601-3102):
 
a. Alanine aminotransferase or aspartate aminotransferase > 2.0 times the upper limit of normal (ULN); or
 
b. Bilirubin (total bilirubin) > 1.5 x ULN (or > 2.0 x ULN if secondary to Gilbert syndrome or pattern consistent with Gilbert syndrome);
 
10. Is currently pregnant or lactating, or intends to become pregnant during the study period or within 1 month after the last dose of study drug, or plans to donate ova during the study period or within 2 months after the last dose of study drug;
 
11. Has a decline in presenting visual acuity score, as defined below (unless explained by refractive error or approved by the sponsor):
 
a. 90 or lower and 5 or more points lower at Week 24/Baseline visit relative to the parent study Baseline visit; or
 
b. The presenting visual acuity score has decreased by ten or more points at the Week 24/Baseline visit relative to the parent study Baseline visit;
 
Note: Visual acuity score must have been obtained with corrective lenses, if applicable.
 
12. Is inappropriate for participation in this study because of conditions that may interfere with interpretation of study results or prevent the patient from complying with study requirements, as determined by the investigator, sub-investigator, or medical monitor;
 
13. Met a withdrawal criterion in the parent study (MVT-601-3101 or MVT-601-3102).
	
Dose and Route of Administration	
Test Product (all patients)
 
 
Relugolix 40 mg tablet will be co-administered orally once daily with 1.0 mg estradiol/0.5 mg norethindrone acetate. The low-dose hormonal add-back therapy will be over-encapsulated. Study treatment will be administered on an empty stomach.
 

Duration of Treatment	
Study treatment will be self-administered for 80 weeks (Open-Label Treatment Period).
 
Concomitant Medicinal Products Systematically Prescribed for All Study Patients
 
Two protocol-specified analgesics include a first-line non-steroidal anti-inflammatory drug and a second-line opioid or opioid/acetaminophen or opioid/paracetamol combination for endometriosis-related pain relief as required. The specific analgesic drugs offered may differ for different countries or regions. The analgesics for each patient will be the same as those prescribed for her during the parent study.

Criteria for Evaluation	
Descriptive assessments of long-term efficacy and safety will be made between the parent study Baseline and Week 52, and between the parent study

	
Baseline and the end of the extension study (Week 104) for the following parent study treatment groups:
 
 
• Parent Study Group A: Randomized to 24 weeks of oral relugolix 40 mg once daily co-administered with 1.0 mg estradiol and 0.5 mg norethindrone acetate in the parent study;
 
• Parent Study Group B: Randomized to 12 weeks of oral relugolix 40 mg once daily followed by 12 weeks of oral relugolix 40 mg once daily co-administered with 1.0 mg estradiol and 0.5 mg norethindrone acetate in the parent study;
 
• Parent Study Group C: Randomized to placebo in the parent study.
 
 
The parent study Baseline will be used as the reference point for this extension study for all change from baseline-related endpoints. The pain scores during the Baseline Pain Assessment Period of the parent study will establish the patient's baseline for both the parent study and the extension study.
 
Primary Efficacy Endpoints
 
Week 52
 
 
• Proportion of women who respond or maintain response at Week 52/Early Termination, based on their dysmenorrhea NRS scores;
 
• Proportion of women who respond or maintain response at Week 52/Early Termination, based on their NMPP NRS scores.
 
 
Week 104
 
 
• Proportion of women who respond or maintain response at Week 104/Early Termination, based on their dysmenorrhea NRS scores;
 
• Proportion of women who respond or maintain response at Week 104/Early Termination, based on their NMPP NRS scores.
 
 
Secondary Efficacy Endpoints
 
To be assessed at Week 52 and Week 104, unless otherwise specified
 
 
• Change from the parent study Baseline in the EHP-30 Pain Domain scores;
 
• Change from the parent study Baseline in the mean dysmenorrhea NRS score;
 
• Proportion of patients who are better or much better on the PGIC for dysmenorrhea (at Week 52 only);
 
• Change from the parent study Baseline in the mean NMPP NRS score;
 
• Change from the parent Baseline in the mean NRS score;
 
• Proportion of patients not using opioids;
 
• Proportion of patients not using analgesics;
 
• Proportion of patients who are better or much better on the PGIC for NMPP (at Week 52 only);
 
• Change from the parent study Baseline in the mean dyspareunia NRS scores;
 
• Proportion of patients who are better or much better on the PGIC for dyspareunia (at Week 52 only);
 

--	---

- Change from the parent study Baseline in the mean dyspareunia functional impairment on the sB&B scale;
- Change from the parent study Baseline in severity scores on the PGA for pain;
- Proportion of responders based on their EHP-30 Pain Domain score;
- Change from the parent study Baseline in function impairment on the PGA for function;
- Change from the parent study Baseline in each of the non-pain EHP-30 domains (Control and Powerlessness, Social Support, Emotional Well-Being, and Self-Image);
- Change from the parent study Baseline pain assessment period in dysmenorrhea-related functional effects (sB&B);
- Change from the parent study Baseline pain assessment period in NMPP-related functional effects (sB&B).

#### Safety Endpoints

To be assessed at Week 52 and Week 104

- Incidence of adverse events;
- Percent change from the parent study Baseline in bone mineral density at the lumbar spine (L1-L4), femoral neck, and total hip as assessed by DXA.

#### Pharmacodynamic Endpoint

To be assessed at Week 52 and Week 104

- Change from parent study Baseline in predose concentrations of serum estradiol.

#### Exploratory Endpoints

To be assessed at Week 52 and Week 104

- Change from Baseline in the EHP-30 scale total score;
- Change from Baseline in the EHP Work Domain score;
- Change from parent study Baseline in the EQ-5D-5L.

### **Statistical Methods**

Efficacy and safety data will be analyzed using descriptive statistics by the originally randomized treatment groups. There will be no between-treatment group comparisons for the extension study data. There will be two analyses: one at Week 52 and one at Week 104. A clinical study report will be generated from each analysis.

#### Efficacy

Efficacy data will be summarized by the original randomized treatment group assigned in the parent study (ie, Parent Study Groups A, B, and C) for the modified Intent-to-Treat Population. The analyses methods for efficacy endpoints are similar to those used for the parent studies, unless otherwise specified in the statistical analysis plan (SAP).

The point estimate and 2-sided 95% confidence interval (CI) for the primary efficacy endpoints (proportion of responders based on dysmenorrhea NRS scores and use of rescue analgesic medications, proportion of responders based on NMPP scores and use of rescue analgesic medications) will be calculated.

The methods for analyzing the additional efficacy endpoints are described in the SAP.

### Safety

Safety assessments will include treatment-emergent adverse events, vital signs and weight, physical examinations, clinical laboratory tests, 12-lead ECG, and bone mineral density with DXA. Safety data analyses will use data from all patients from the parent studies who receive any amount of study drug (ie, from parent study Baseline to Week 52 or Week 104).

Drug exposure will be summarized by descriptive statistics. Severity of all treatment-emergent adverse events will be evaluated by the investigator based on the National Cancer Institute Common Terminology Criteria for Adverse Events (CTCAE) and will be coded to preferred term, high level term, and system organ class using the Medical Dictionary for Regulatory Activities (MedDRA). The number and percentage of patients with adverse events will be presented by MedDRA system organ class and preferred term, relationship to study drug, and severity. Laboratory values will be classified by toxicity grade based on the National Cancer Institute CTCAE. Laboratory shift tables of the parent study Baseline results to each of the subsequent visits will be produced.

Bone mineral density will be evaluated in all patients at the lumbar spine (L1-L4), femoral neck, and total hip at the Week 24/Baseline, Week 36, Week 52, and Week 104/Early Termination visits. The absolute change and percent change from parent study Baseline and Z-scores will be summarized by visit and parent study treatment group.

The mean percentage change from parent study Baseline to Week 52 in bone mineral density and corresponding 95% CI will be provided for each treatment group. For patients who were randomized to 24 weeks of treatment with relugolix and add-back in the parent studies (Group A in MVT-601-3101 or MVT-601-3102) and enrolled in the extension study, the lower bound of the 95% CI for mean percentage change at Week 52 from parent study Baseline in bone mineral density lumbar spine (L1-L4) will be compared with a pre-specified clinically acceptable threshold of -2.2% to evaluate magnitude of bone mineral density loss after 52 weeks of treatment. If the lower bound is > -2.2%, bone mineral density loss for the relugolix add-back treatment will be considered insignificant. The 95% CI for mean percentage change at Week 104 from parent study Baseline in bone mineral density lumbar spine (L1-L4) will be provided along with descriptive statistics for bone mineral density loss at Week 104 as supportive analyses.

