### **9.2. Analysis Populations**

Efficacy data analyses will be performed on the modified Intent-to-Treat (mITT) Population, defined as all patients who were randomized in a parent study (MVT-601-3101 or MVT-601-3102) and who have received any amount of randomized study drug.

Safety data analyses will be performed on the Safety Population, defined as all patients who were randomized in a parent study and who have received any amount of randomized study drug.

The analysis methods for safety and efficacy endpoints are the same as those used for the parent studies, unless otherwise specified in the SAP.

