## 9.5. Safety Analyses

Safety assessments will include treatment-emergent adverse events, vital signs and weight, physical examinations, clinical laboratory tests, 12-lead ECG, and bone mineral density with DXA. Safety summaries by treatment group will be performed using treatment groups defined based on the actual randomized treatment received in the parent study.

The treatment-emergent period will be defined as the period of time from the first dose date and time of randomized study drug in the parent study through 30 days after the last dose of study drug, or the date of initiation of another investigational agent or hormonal therapy affecting the hypothalamic-pituitary-gonadal axis or surgical intervention for endometriosis, whichever occurs first. Safety will be assessed through summaries of adverse events, the frequency of treatment discontinuations due to adverse events, laboratory evaluations, and bone densitometry results.

The severity of all adverse events is to be evaluated by the investigator based on the National Cancer Institute CTCAE. All adverse events will be coded to preferred term, high level term, and system organ class using MedDRA 20.0 or higher. The incidence of adverse events will be presented by MedDRA system organ class and preferred term, relationship to study drug treatment, and severity. A patient reporting the same adverse event more than once is counted once, and at the maximum severity or strongest relationship to study drug treatment when calculating incidence.

Laboratory data consist of chemistry, hematology, and hormonal tests. Only data collected by the central laboratory will be used to do the analyses. The National Cancer Institute CTCAE will be used to categorize toxicity grade for the laboratory parameters. Shift tables will be provided for each gradable parameter to summarize baseline toxicity grade versus post-baseline toxicity grade. For laboratory parameters that are not gradable by the CTCAE, a shift table based upon the normal range (low, normal, and high) will be provided for each parameter to summarize the parent study Baseline versus post-baseline results. All data will be listed and summarized by

visit. The change from parent study Baseline to each post-baseline study visit will be presented by parent study treatment group for each laboratory test.

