### Sample Size Estimation

Because this is an extension study, the sample size will be determined by the number of patients who have completed a parent study (MVT-601-3101 or MVT-601-3102) and who are eligible and willing to participate in the extension study. It is estimated that approximately 800 patients (67% of the total of 1200 patients who will be randomized into the parent studies) will participate in this study.

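### Adverse-event percentages at Week 52 and Week 104 use everyone dosed in a parent study as denominator, which dilutes late-onset events because about one third are not expected to be followed past about Week 28

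*Protocol*

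**What the plan says.** **Population.** The Safety paragraph of the synopsis says that "Safety data analyses will use data from all patients from the parent studies who receive any amount of study drug", and gives the span as parent-study Baseline to Week 52 or Week 104. Section 9.2 agrees: the Safety Population is "defined as all patients who were randomized in a parent study and who have received any amount of randomized study drug". Neither place requires entry into the extension.

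**Measure.** In the synopsis, "The number and percentage of patients with adverse events will be presented by MedDRA system organ class and preferred term", and also by relationship and severity. Section 9.5 adds the counting rule: "A patient reporting the same adverse event more than once is counted once". The result is a simple proportion of patients. Drug exposure is summarized descriptively, as a separate item.

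**Time points.** Incidence of adverse events heads the safety endpoints, under the line "To be assessed at Week 52 and Week 104". Each time point has its own study report.

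**Observation.** Section 9.5 runs the treatment-emergent period from the first randomized dose "through 30 days after the last dose of study drug", or to the start of certain other treatments or endometriosis surgery if that comes first.

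**Expected entry.** Sample Size Estimation expects "approximately 800 patients (67% of the total of 1200 patients who will be randomized into the parent studies") to take part.

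**Objective.** The safety objective in Section 3 concerns up to 104 weeks of treatment in women who completed the 24-week parent treatment, a narrower group than the Safety Population.

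**The concern.** A crude percentage is easy to read when everyone in the denominator is followed for about the same time. The parent studies had one common 24-week treatment period. Here the same measure is applied to women whose observation ends at most about 28 weeks after first dose and to women followed for up to 104 weeks. The first group stays in the denominator of a figure labelled Week 52 or Week 104 but can add nothing to the numerator after about Week 28.

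Late-emerging and steadily accumulating harms are what a two-year extension is meant to describe, and they are the ones diluted. This does not depend on which active regimen a woman had in the parent study, so it affects Groups A and B as well as C.

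The protocol treats its other safety endpoint differently. In the synopsis, the Group A bone-density threshold analysis is confined to women enrolled in the extension. Section 9.5 also plans to relate bone loss to treatment exposure. The text shown gives adverse events neither treatment.

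**Working it through.** **Inputs from the protocol**
- Randomized in the parent studies: 1200. Expected to enter: 800 (Sample Size Estimation).
- Parent treatment: 24 weeks = 168 days. Treatment-emergent window: 30 days after last dose (Section 9.5).
- Reporting times: Week 52 and Week 104.

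**Assumptions, not in the protocol**
- The entry share is the same in each parent group.
- Non-entry is unrelated to later adverse-event risk.
- The hazard is constant.
- There is no dropout after entry.
- Every non-entrant is observed for the full window. This is generous, since women who left a parent study early are observed for less.

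**Step 1, the plan's own figure.** 800/1200 = 66.7%, which reproduces the stated 67%. Non-entrants: 400/1200 = 33.3%.

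**Step 2, last possible treatment-emergent day for a non-entrant.** (168 + 30)/7 = 28.3 weeks.

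**Step 3, mean observed time per woman in the denominator.** (2/3)T + (1/3)(28.3):
- T = 52: 34.67 + 9.43 = 44.1 weeks, or 85% of 52.
- T = 104: 69.33 + 9.43 = 78.8 weeks, or 76% of 104.

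**Step 4, what a true 10% cumulative risk looks like.** With hazard λ = −ln(0.9)/T, the crude figure is (2/3)(0.10) + (1/3)[1 − exp(−28.3λ)].

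| | λ per week | Risk by Week 28.3 | Crude percentage | Ratio to true |
|---|---|---|---|---|
| Week 52 | 0.10536/52 = 0.002026 | 5.57% | 6.67% + 1.86% = 8.5% | 0.85 |
| Week 104 | 0.10536/104 = 0.001013 | 2.82% | 6.67% + 0.94% = 7.6% | 0.76 |

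Counting the final 30-day window at the end of the study (T = 108.3 weeks) gives 7.57%, so the Week 104 result does not change.

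**Step 5, sensitivity.**
- True risk from 1% to 50%: ratio 0.85 to 0.88 at Week 52, and 0.76 to 0.78 at Week 104.
- Assumed dropout of 15% to 30% after entry, placed midway between Week 24 and the reporting time, with a true risk of 10%: ratio 0.83 to 0.80 at Week 52, and 0.72 to 0.69 at Week 104.
- Onset only after Week 28: ratio 2/3 at both times, so 10% among the women still observed is shown as 6.7%.
- Onset only by Week 24: ratio 1.0, no dilution.

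**Step 6, would an entrants-only percentage over the whole period be a safe replacement?** Suppose early events occur in 10% of entrants and 20% of non-entrants, and a further 5% of entrants have a late event. The all-dosed figure is (800 × 0.15 + 400 × 0.20)/1200 = 200/1200 = 16.7%. The entrants-only figure is 15.0%. Here the replacement looks more favourable, because it discards the women with more early events.

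**The case against.** **All-dosed is a defensible population.** It keeps women who stopped early because of adverse events. Entrants are selected: they must have completed 24 weeks, and women with a bone-density loss of 7% or more, raised liver tests or a met parent-study withdrawal criterion are excluded. This stands. It is a reason to keep the planned table and not to put entrants-only percentages in its place.

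**Exposure-adjusted rates are usual SAP content.** Section 9 leaves detailed methods to the SAP, and Section 9.2 carries over the parent-study methods unless the SAP says otherwise. This stands in part. The SAP was not available for this review and may already add such tables. The all-dosed population and the percentage measure, however, are fixed in the protocol itself, and carrying over methods from studies with one common treatment length is the source of the difficulty.

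**Only part of the text is current.** Sections 9.2 and 9.5 are available only as Amendment 2 text. The later protocol version breaks off in Section 6.5.2.6. Its synopsis repeats the population and the measure, so the core survives. The denominator of the adverse-event table is still an inference, because it is not written out. A reader might conclude that the crude percentage is the only adverse-event measure planned; the text shown cannot support that.

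**The direction is not universal.** A reader might infer that every long-term percentage is understated. Events starting by Week 24 are not, and Step 6 shows that the all-dosed figure can exceed the entrants-only one. The understatement is against cumulative incidence at Week 52 or 104 under the stated assumptions.

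**Comparability.** It would also go too far to say that the Week 52 and Week 104 figures cannot be set side by side. With a fixed denominator they are cumulative counts in the same women, and the difference is the newly affected women. What they lack is a reading as one- or two-year risk.

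**Conclusion.** The point holds as a limited one. Read as written, the plan dilutes adverse events that start or keep accruing after about Week 28. The relative shortfall is about 15% at Week 52 and 24% at Week 104 under a constant hazard, one third for events starting after Week 28, and nil for events starting by Week 24.

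These sizes rest on the assumptions listed with the calculation. The weakest is equal entry by group: the 67% is a pooled planning estimate of randomized, not dosed, women, and it is not split by parent group. Dropout after entry would widen the gap. Non-entry related to risk could move it either way.

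The adverse-event summaries are descriptive, and no prespecified decision depends on them, so the trial's conclusions are not overturned. What is missing from the protocol text is an adverse-event summary that can be read as risk over one or two years of treatment. In Group C the time at risk also includes placebo weeks; that is a separate question and does not enter the figures here.

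**What to change.** Keep the all-dosed cumulative table as planned, and add to Section 9.5, for both reports:

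1. First-event incidence in the Safety Population by parent-study group, either exposure-adjusted (for example per 100 patient-years) or by a time-to-event method, with each woman's own treatment-emergent time at risk.
2. A table of adverse events with onset on or after the first extension dose, with the women enrolled in the extension as denominator. This matches the point at which the Schedule of Activities starts adverse-event collection under this protocol.

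Do not replace or demote the all-dosed table with entrants-only percentages over the whole period, since that would drop the women who stopped early. If the SAP already contains both additions, a sentence in Section 9.5 pointing to them is enough.

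The cost is a few lines of wording and one extra table set, with no new data collection. Some long-term figures may look less favourable than the crude percentages.
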